5.6 Duration of Follow Up

Patients will either be seen in the clinic, or contacted by phone every 3 months for 1 year post study treatment.

Follow up data to be collected:

- Survival status
- Disease status (progressed/stable)
- If any additional cancer therapy was initiated (name & start date)

Patients removed from study for unacceptable adverse event(s) will be followed until resolution or stabilization of the adverse event.

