5.5 Duration of Therapy

In the absence of treatment delays due to adverse event(s), treatment may continue until one of the following criteria applies:

- Disease progression for patients on ARM B (Patients who develop progression on ARM A may be crossed-over to ARM B after re-registering patient with coordinating center). Disease progression in this case is defined as 20% increase in sum of index lesions compared with baseline (not the best response); or unequivocal diagnosis of new non-bony tumor lesion. Patients who are noted to have ‘new’ or ‘worsening’

bony lesions can stay on treatment if the patient has clinical benefit (it has been challenging to diagnose bony metastasis response/progression while patients are treated with such new class of drugs).

- Off of study drug continuously for more than 28 days for any reason.
- Intercurrent illness that prevents further administration of treatment,
- Unacceptable adverse event(s) or meets any dose stopping criteria (Section 6)
- Patient decides to withdraw from the study, or
- General or specific changes in the patient's condition render the patient unacceptable for further treatment in the judgment of the investigator.

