- j. Patients on both ARMs must have a dermatologic exam to monitor and manage side effects on the skin.
- k. All patients must have ophthalmologic exam at pre-therapy. Patients randomized to or crossed over to ARM B (combination treatment arm) should have these as clinically indicated. Patients are required to have a standard ophthalmic exam performed by an ophthalmologist at baseline, and as clinically warranted per protocol's guidance (Refer to Section 6.2.2 for visual changes stopping criteria). The exam will include indirect fundoscopic examination, visual acuity (corrected), visual field examination, tonometry, and direct fundoscopy, with special attention to retinal abnormality that are predisposing factors for RVO or CSR. For patients with clinical suspicion of RVO or CSR, fluorescein angiography and/or optical coherence tomography are highly recommended.
- l. Each cycle start is allowed a +/- 3 day window
- m. Patients taking Antiplatelets or Anticoagulants need to have a CBC every 2 weeks for the first 4 months.
- n. Patients that cross over from ARM A to ARM B are not eligible for the PK or PGx correlative studies.
- o. All patients will receive a follow up phone call a week after each clinic visit for the first 4 months of treatment. The team will confirm with the patient that they are taking the correct amount of study medication, and that they have enough study medication to last until their next clinic visit.
- p. After the completion of the 18th cycle, visits will be extended to every 8 weeks. All exams, tests, and scans listed for the odd cycle visits will be completed.
- q. Electrocardiogram (EKG) will be done pre-study and every 2 cycles for 6 cycles and then every 4 cycles x 18 months and then only if clinically indicated.
- r. After completion of the 18th cycle, visits will be extended to every 8 weeks. BRAF research labs will be drawn at every other visit (every 16 weeks) and at time of progression.

Baseline evaluations are to be conducted within 4 weeks prior to start of protocol therapy. Four weeks (28 days) is considered one cycle. A member of the study team will be making a follow up phone call to each patient a week after each clinic visit for the first 4 months of treatment. The team will confirm with the patient that they are taking the correct amount of study medication, and that they have enough study medication to last until their next clinic visit.

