In general, patients are followed every 2 weeks for the first 8 weeks and then every 4 weeks until the completion of cycle 18 at which time visits will be extended to every 8 weeks while on study. Off therapy visit is done within 4 weeks after last dose of study drug. Additionally, patients will be seen in the clinic, or contacted by phone every 3 months for 1 year post study treatment.

Follow up data to be collected:

- Survival status
- Disease status (progressed/stable)
- If any additional cancer therapy was initiated (name & start date)

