13.4 Analysis of Secondary Endpoints

The MR+PR+CR response rate will be estimated for each treatment arm. In determining this rate, the number of patients with RECIST-based MR, PR or CR will be divided by the number of evaluable patients. All evaluable patients will be used for this analysis. Exact binomial 95% confidence intervals for the true PR+CR response rate will be calculated.

The Kaplan-Meier method will be used to estimate progression-free and overall survival. Each of these variables will be measured from the date of registration to the date of the event (i.e., death or disease progression) or the date of last follow-up to evaluate that event. We will also evaluate the proportion of patients who are progression-free and alive at one year.

Toxicity and Tolerability: Frequency and severity of adverse events and tolerability of the regimen in each of the treatment arms will be collected and summarized using descriptive statistics. As per NCI CTCAE v4.0, the term toxicity is defined as adverse events that are classified as either possibly, probably, or definitely related to study treatment. The maximum grade for each type of toxicity will be recorded for each patient, and frequency tables will be reviewed to determine toxicity patterns. In addition, we will review all adverse event data that is graded as 3, 4, or 5 and classified as either “unrelated” or “unlikely to be related” to study treatment in the event of an actual relationship developing. The incidence of severe (grade 3+) adverse events or toxicities will be described. We will also assess tolerability of the regimens through assessing the number of patients who required dose modifications and/or dose delays. In addition, we will also capture the proportion of patients who go off treatment due to adverse reactions or even those who refuse further treatment for lesser toxicities that inhibit their willingness to continue participation on the trial. These tolerability measures will be assessed within each of the treatment arms and we will explore differences in these measures between the arms. All patients who have received at least one dose of any of the therapeutic agents in a treatment arm will be evaluable for toxicity and tolerability.

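### Survival contact stops one year after each patient's own treatment end, so overall survival beyond month 12 rests on fewer patients and is potentially informatively censored

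*Combined protocol and SAP*

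**What the plan says.** Section 5.6 has patients seen in clinic or "contacted by phone every 3 months for 1 year post study treatment", and lists survival status among the data collected. The text closing Section 10 repeats the rule: "Additionally, patients will be seen in the clinic, or contacted by phone every 3 months for 1 year post study treatment". No section sets longer survival contact, a later survival sweep or a common OS cut-off.

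Section 1.2 makes OS for each treatment group a secondary objective. Section 13.4 states: "The Kaplan-Meier method will be used to estimate progression-free and overall survival". Time runs from registration to the event "or the date of last follow-up to evaluate that event". The same section adds: "We will also evaluate the proportion of patients who are progression-free and alive at one year".

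Section 13.2 expects about 24 months of accrual and a 4-year study, so that clinical outcomes can be fully evaluated. The treatment-stop reasons in Section 5.5 include progression, intercurrent illness, and changes in condition that "render the patient unacceptable for further treatment in the judgment of the investigator". Section 5.5 also allows cross-over: "Patients who develop progression on ARM A may be crossed-over to ARM B after re-registering patient with coordinating center".

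**The concern.** The end of survival contact is tied to each patient's treatment stop, not to a calendar date. Early entrants and early stoppers leave observation long before the study ends, and their later deaths never enter the Kaplan-Meier curve.

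This matters in two ways. The first needs no assumption about direction: fewer deaths are seen and fewer patients are at risk, so late OS is less precise. The second is conditional. Kaplan-Meier needs censoring to be unrelated to later risk of death. If patients who stop treatment differ in risk from those still on it, censoring them 12 months after stopping distorts the curve. Several stop reasons carry prognostic meaning; others, such as more than 28 days off drug or withdrawal, have no stated direction. What is at stake is a descriptive secondary estimate.

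**Working it through.** **Inputs from the plan.** Contact ends 12 months after treatment stop (5.6, 10); OS runs from registration (13.4); accrual about 24 months, study 48 months, 26 per arm (13.2).

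**Assumed, because the documents give no stopping times or hazards for this trial.** Exponential times; median time to stop 11 or 16 months; median survival after stopping 18 months; r = death hazard after stopping divided by death hazard on treatment, from 1 to infinite (no on-treatment deaths).

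**Step 1: the plan's own figure.** The plan states nothing on OS precision. Its 90% probability of correct selection (13.1.3) reproduces: P(difference ≥ 0.10) + 0.5 × P(|difference| < 0.10) at 15% vs 35% is 0.8138 + 0.5 × 0.1805 = 0.904. It concerns response within 6 cycles and contains no survival term.

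**Step 2: the unobserved gap.** A patient who enters at calendar month e and stops after s months is in contact until month e + s + 12. The gap to study end is 48 − (e + s + 12) = 36 − e − s, if positive.
- e = 0, s = 6: gap 30 months; last contact is 18 months after registration.
- e = 24, s = 6: gap 6 months.
- e = 24, s = 12: no gap.

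**Step 3: month 12.** Treating registration and first dose as the same day (Section 4.1 allows 5 business days), the rule censors at s + 12 ≥ 12 months. OS to month 12 is therefore the same under both follow-up schemes.

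**Step 4: at risk at month 24, closed form, stop median 11.**
- r = 1: survival to month 24 is 2^(−24/18) = 0.397, and 26 × 0.397 = 10.3. Being in contact also requires stopping after month 12, with probability 2^(−12/11) = 0.469. So 10.3 × 0.469 = 4.8.
- r = 2: let λ = ln2/11 = 0.0630, h0 = ln2/18 = 0.0385 and h1 = h0/2 = 0.0193. Alive and on treatment: e^(−24(λ+h1)) = 0.139. Alive after stopping: the integral of λ·e^(−(λ+h1)u)·e^(−h0(24−u)) over stop times u, which is 0.372 for u from 0 to 24 and 0.138 for u from 12 to 24. Full follow-up: 26 × (0.139 + 0.372) = 13.3. Under the rule: 26 × (0.139 + 0.138) = 7.2.

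**Step 5: simulation.** 20,000 arms of 26; each pair is one-year rule / follow-up to study end. At-risk values agree with the closed form to within 0.1.

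| r | Stop median | Deaths seen | Unseen | At risk, month 24 | Fall | SD of 24-month OS (points) |
|---|---|---|---|---|---|---|
| infinite | 11 | 8.0 / 13.4 | 40% | 10.8 / 17.5 | 38% | 9.9 / 9.2 |
| infinite | 16 | 6.9 / 11.1 | 38% | 14.1 / 19.3 | 27% | 8.7 / 8.6 |
| 4 | 11 | 10.5 / 15.4 | 32% | 8.8 / 15.2 | 42% | 10.8 / 9.7 |
| 4 | 16 | 10.1 / 14.1 | 28% | 11.4 / 16.4 | 30% | 10.1 / 9.5 |
| 2 | 11 | 12.4 / 17.0 | 27% | 7.2 / 13.2 | 45% | 11.0 / 9.8 |
| 2 | 16 | 12.6 / 16.2 | 22% | 9.3 / 14.0 | 34% | 10.5 / 9.7 |
| 1 | 11 | 15.1 / 19.3 | 22% | 4.8 / 10.3 | 53% | 11.3 / 9.6 |
| 1 | 16 | 16.0 / 19.2 | 17% | 6.2 / 10.4 | 40% | 10.8 / 9.7 |

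The SD rises by 0.1 to 1.7 points. Shorter treatment would cost more. With a median of 5.8 months on treatment (the placebo progression-free survival (PFS) median that Section 2.1 cites from the sorafenib trial) and other survival assumptions, the standard error at month 24 reached 13.6 points, against at most 10.1 with full follow-up.

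**Step 6: bias at month 24.** In this model the bias is +2.2 to +2.5 points at r = 4, +1.4 to +1.5 at r = 2, zero at r = 1, and −1.7 to −1.8 at r = 0.5. A different model, in which early stopping predicts shorter survival, gives +3.5 to +7. The documents do not choose among these.

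**The case against.** The best defence is that nothing here is an error. Sections 5.6, 10 and 13.4 agree with one another, Kaplan-Meier is built for unequal follow-up, OS has no hypothesis, event target or planned comparison, and 24 months of accrual + 12 on treatment + 12 of contact = 48. The loss of deaths also sounds larger than its effect: at month 24 the SD changes by less than 2 points in the tabulated cases, when a 95% interval with 26 patients is already roughly ±20 points.

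Most of this stands, and it sets the severity. The 48-month sum does not answer the point: it fits only a patient who enters last and stays on treatment for 12 months. By Step 2, anyone with e + s below 36 months is lost before study end.

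Three stronger readings are tempting, and the documents support none of them:
- **That OS is overstated.** This needs a higher death hazard after stopping than on treatment. That is plausible, but no hazards are given, and the bias could be zero or negative.
- **That the arms are followed unequally, with a known effect.** If the contact year starts after cross-over therapy, Arm A patients who cross over are followed longer from their first stop. The starting point is not spelled out, and cross-over rates and durations are not given, so no size can be attached.
- **That OS should be read only to month 12.** This would discard usable later estimates. Month-36 figures, however, depend too heavily on assumptions to be relied on in either direction.

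**Conclusion.** The point holds at low severity. The follow-up rule leaves deaths unobserved and thins the risk set after month 12, in a study long enough to capture many of those deaths. The illustrative size is 17-40% of deaths by study end unseen, 27-53% fewer at risk at month 24, and an SD of 24-month OS higher by about 0-2 points. These figures rest on exponential times, stop medians of 11 or 16 months and a post-stop median of 18 months. That information is lost follows from the rule itself. Informative censoring is a possibility, with direction and size unknown and model-dependent.

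OS to month 12, the primary endpoint, the 0.10 selection rule and the one-year progression-free-and-alive proportion are unaffected. Late PFS, one of the factors considered when response rates fall within 0.10, could be touched marginally: patients who stop without progression also lose disease-status contact after a year.

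**What to change.** In Section 5.6 and the matching text of Section 10, for example:

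> Survival status and subsequent therapy will be collected by phone or record check every 3 months until death, withdrawal of consent or the common study end, whatever the date of treatment stop or cross-over.

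In Section 13.4:

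> OS is censored at the common cut-off, or at last contact if earlier; numbers at risk are reported.

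The cost is a short amendment, some extra time of existing site staff for at most 52 patients, and possibly updated consent (the consent pages are not in the public text, so this cannot be checked). No visits or scans are added.

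If the one-year rule is kept, report numbers at risk, state that OS beyond month 12 is potentially informatively censored, and say whether the contact year starts after cross-over therapy. If it does, note that follow-up may differ by arm.

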5.7 Criteria for Removal from Study

Patients will be removed from study when any of the criteria listed in Section 5.5 applies. The reason for study removal and the date the patient was removed must be documented in the Case Report Form.

6. DOSING DELAYS/DOSE MODIFICATIONS

6.1 Dabrafenib Delays/Modifications (applicable to ARM A and ARM B patients):

For Arm B patients, please see section 6.2 also.

6.1.1 Guidelines for Dabrafenib Dose Modification and Treatment of Adverse Events

The severity of adverse events will be graded utilizing the Common Terminology Criteria for Adverse Events Version 4.0 (CTCAE v4.0). Dose modifications of Dabrafenib will be made according to the dose levels outlined in **Table 1**.

Table 1. Dabrafenib Dose Levels

| Dose Level | Dabrafenib Dose/Schedule |
|-------------------|---------------------------------|
| 0 | 150 mg BID |
| - 1 | 100 mg BID |
| - 2 | 75 mg BID |
| - 3 | 50 mg BID |

Guidelines for dose modifications and interruptions for management of toxicities associated with the study treatment other than those pertaining to neutropenia, fever, rash, hand foot skin reactions (HFSR), renal insufficiency, liver chemistry abnormalities, left ventricular ejection fraction (LVEF) are provided in **Table 2**.

Dose modifications specifically for neutropenia are outlined in **Table 3**. Prophylactic antibiotics are recommended for treatment of neutropenic fever (defined as a single fever $>38.3^{\circ}\text{C}$ (101°F), or a sustained temperature $>38^{\circ}\text{C}$ (100.4°F) for more than one hour in a patient with absolute neutrophil count (ANC) <500 cells/microL, or <1000 cells/microL with a predicted nadir of <500 cells/microL). The choice of antibiotic for neutropenic fever is per the treating physician and the institution's hospital policy.

Dose modifications for fever are provided in **Table 4**. Antipyretic use is permitted for symptomatic relief of fever. In the absence of severe neutropenia, the use of antibiotics is at the clinical discretion of the examining physician/investigator. For complicated fever, defined as Grade ≥ 3 fever or any grade with signs and symptoms including; rigors, dehydration, hypotension, dizziness or weakness, the administration of both Dabrafenib and Trametinib should be interrupted/held.

Dose modifications for rash and general recommendations for rash management are provided in **Table 5**.

Dose modifications for hand foot skin reaction (HFSR) are provided in **Table 6**. Treatment of squamous cell carcinoma (SCC), keratoacanthoma (KA), and actinic keratosis (AK) lesions should be based upon institutional practice. Dose interruptions or modifications are usually not required for SCC/KA. Biopsies of any new skin lesions suspicious for malignancy and pre-malignancy (SCC, AK, KA) are recommended.

Dose modifications for renal insufficiency are outlined in **Table 7**.

Table 2. Dose Modification Table for Toxicities Other Than **Neutropenia, Fever, Rash, HFSR, LVEF, renal insufficiency or liver chemistry abnormalities

| Non-hematologic and hematologic Toxicity (except**) | Dose Modification Algorithms ^{a, b, d, e} |
|---|---|
| Grade 1 | Continue Dabrafenib at full dose, monitor as clinically indicated. |
| Grade 2 | 
For Grade 2 Diarrhea with accompanying risk factors^c Hold Dabrafenib until return to \leq Grade 1, provide supportive care.
 
All other toxicities: Consider holding Dabrafenib until resolution to Grade 1 or baseline; provide supportive care as clinically indicated. Monitoring of laboratory values should occur as clinically indicated.
 
For Grade 2 or higher respiratory symptoms (i.e. cough, dyspnea, hypoxia etc.), evaluation by a CT scan is recommended.
 |
| Grade 3 | 
For Grade 3 toxicity, hold Dabrafenib until toxicity is Grade 1 or baseline then reduce dose of Dabrafenib by 1 dose level. The subject may be continued at the same dose if, in the judgment of the investigator, the toxicity is considered to be unrelated to Dabrafenib. Continue to monitor as clinically indicated.
 
If any Grade 3 toxicity recurs, hold dosing until Grade 1 or baseline, then reduce current dose of Dabrafenib by one dose level.
 |
| Grade 4 | 
Discontinue Dabrafenib. Continue to monitor as clinically indicated, and provide supportive care as needed
 
If in the investigator's judgment the toxicity is unlikely to recur then, hold until toxicity is Grade 1 or baseline, then reduce dose of Dabrafenib by 1 dose level. If Grade 4 toxicity recurs after dose reduction, discuss continuation of study drug with the PI.
 |

** Neutropenia, Fever, Rash, HFSR, LVEF, renal insufficiency or liver chemistry abnormalities

- The minimum dose is 50 mg BID. If a subject requires dose reduction below 50 mg BID then the subject must be discontinued from study medication.
- For adverse events of abdominal pain or suspected pancreatitis, amylase and lipase laboratory samples should be collected.
- Risk factors for cancer treatment-induced diarrhea include: fever, orthostatic symptoms (i.e. dizziness), abdominal pain/cramping, or weakness.
- If the patient has a Grade 3 or 4 laboratory abnormality, that in the judgment of the investigator, is not considered clinically significant, dose modification is not required.
- For subjects who develop symptoms associated with uveitis including blurry vision, eye pain or erythema ophthalmologic consult is required.

Table 3. Dose Modification Table for Neutropenia

| Grade | ANC value /mm3 | Management of Neutropenia | Dabrafenib Dose Adjustment |
|-------|----------------|---|---|
| 1 | 1500-LLN | 
 Monitor per protocol time and events table | Continue at current dose |
| 2 | 1000-<1500 | 
 Re-check ANC in 1 week. If improvement to grade 1, continue to monitor per protocol time and events table. If stable at grade 2, monitor ANC every 2 weeks until resolution to grade 1 or until stable for 4 weeks If worsens to grade 3 or 4 follow below. | Any occurrence: continue at current dose |
| 3 | 500-<1000 | 
 Re-check ANC at least weekly during dose interruption. If resolved to grade 1, re-check ANC 3 days after rechallenge with Dabrafenib and then 1 week later. | 
 Any occurrence: hold until return to grade 1, then reduce one dose level 1st recurrence: Discontinue Dabrafenib or hold until return to grade 1, then reduce one dose level 2nd recurrence: Discontinue Dabrafenib. |
| 4 | <500 | 
 Re-check ANC at least weekly If resolved to grade 1, re-check ANC 3 days after rechallenge with Dabrafenib and then 1 week later. | 
 Discontinue or hold until return to grade 1, then reduce Dabrafenib by one dose level. 1st recurrence: discontinue Dabrafenib. |

Table 4. Dose Adjustments for Fever (Pyrexia) ^{a, b}

| Occurrence | Management | Study drug adjustment |
|-----------------------------|---|---|
| 1st event | 
 • Clinical evaluation for infection and hypersensitivity^c • Laboratory work-up^c • Hydration as required^d | 
 • Administer anti-pyretic treatment if clinically indicated^e • Continue or Interrupt dabrafenib depending on severity of pyrexia and associated conditions-for example, if fever was associated with dehydration, hypotension, or renal insufficiency, hold dabrafenib and reduce dabrafenib by one dose level when restarted. • Once pyrexia resolves to baseline, restart dabrafenib at the same dose if dabrafenib was held. |
| 2nd event | 
 • Work-up at physicians' discretion | 
 • Same as for 1st event and: 
 • Administer anti-pyretic treatment if clinically indicated^f • Consider oral corticosteroids (i.e., prednisone 10 mg/d) for at least 5 days or as clinically indicated^f |
| Subsequent events | 
 • Work-up at physicians' discretion | 
 • Same as for 1st event and: 
 • Administer anti-pyretic treatment if clinically indicated^e • Optimize oral corticosteroid dose as clinically indicated for recalcitrant pyrexia^f • If corticosteroids have been tapered and pyrexia recurs, restart steroids • If corticosteroids cannot be tapered or escalating doses are required, consult protocol chair. • If associated with dehydration, hypotension or renal insufficiency (on 2 or more occasions), reduce dabrafenib by one dose level |

BUN = blood urea nitrogen;

a. Fever (pyrexia) is defined as a body temperature equal to or above 38.5° Celsius or 101.3° Fahrenheit.

- b. For subjects experiencing fever (pyrexia) complicated by rigors, severe chills, etc., a clinical evaluation is mandatory for each event; anti-pyretic treatment should be started immediately at the first occurrence and prophylactic anti-pyretic treatment is recommended
- c. Thorough clinical history for symptoms of infection or hypersensitivity is required; laboratory work-up may include complete-blood-count, electrolytes, creatinine, BUN, liver-function tests, blood culture, and urine culture.
- d. Oral hydration should be encouraged in subjects without evidence of dehydration. Intravenous hydration is recommended in subjects experiencing pyrexia complicated by dehydration/hypotension.
- e. Anti-pyretic treatment may include acetaminophen (paracetamol), ibuprofen, or suitable anti-pyretic medication according to institutional standards. Prophylactic anti-pyretic treatment may be discontinued after three days in the absence of pyrexia
- f. In subject experiencing pyrexia complicated by rigors, severe chills, etc., which cannot be controlled with anti-pyretic medication, oral corticosteroids should be started at the 2nd event and prednisone doses should be gradually increased for subsequent events.

Table 5. Dose Modification for Skin Rash

| Skin Toxicity Grade (CTCAE v 4.0) | Guideline for Management | Dose Reduction^a |
|--|---|---|
| 1 | Topical corticosteroids (mometasone, betamethasone, or fluocinonide creams) | None |
| 2 | Topical steroids with the addition of diphenhydramine 50 mg bid, consider oral prednisone ^b (short course) | None: if unacceptable to subject or medically concerning then hold until recovery to ≤Grade 1. Restart at same dose. |
| ≥3 | | Hold until recovery to ≤Grade 1. Then reduce the dose by one dose level. For subjects with Grade 3 or 4 extensive or symptomatic dermatologic event, or chronic, persistent or recurring lower grade skin events, dermatology consult is encouraged. |

a. If no recovery after 2 weeks of holding drug, subjects must be withdrawn from study treatment unless in the opinion of the investigator there is a reason to believe that the subject will experience clinical benefit from future treatment.

b. The use of topical corticosteroids are preferred except in the event of severe skin toxicity(ies) to avoid the potential drug-drug interaction between the investigational agents and corticosteroids; at physician's discretion

Table 6. Dose Modifications for Hand-Foot Skin Reaction (HFSR)

| HFSR Grade | Occurrence | Dose Modification ^a |
|--------------------------------|---|--|
| 1 | Any occurrence. | Continue treatment with Dabrafenib and start topical therapy ^b for symptomatic relief. |
| 2 | 1st occurrence. | Continue treatment with Dabrafenib and start topical therapy ^b for symptomatic relief. Instruction on life-style modifications should also be given. ^c If no improvement within 28 days, see below |
| | No improvement within 28 days or additional occurrence. | Interrupt Dabrafenib treatment until toxicity resolves to Grade 0-1. ^d When resuming treatment, decrease Dabrafenib dose by one dose level. Continue topical therapy ^b for symptomatic relief. Instruction on life-style modifications should also be given. ^c |
| Grade 3 or intolerable grade 2 | 1st or 2nd occurrence. | Interrupt Dabrafenib treatment until toxicity resolves to Grade 0-1. ^d When resuming treatment, decrease Dabrafenib dose by one dose level. Continue topical therapy ^b for symptomatic relief. Instruction on life-style modifications should also be given. ^c |
| | 3rd occurrence. | Discontinue Dabrafenib treatment. |

- a. No dose adjustment is required on the basis of subject age, gender, or body weight.
- b. Topical therapy includes the following options; keratolytics (e.g. urea 40%), high potency corticosteroids (fluocinonide, clobetasol), oral analgesia (NSAIDs or narcotics)
- c. Lifestyle modifications include; avoidance of excessive temperatures, exercise, and ill-fitting clothing/shoes. Use of soft slippers (Tempurpedic or Crocs), friction-relieving measures (calfskin, gels).
- d. HSFR usually resolves within 2-4 weeks of drug cessation.

Table 7. Dose Modifications and Guidelines for Renal Insufficiency

| Serum Creatinine | Guidelines for Management |
|--|---|
| For subjects with serum creatinine increase >0.2 mg/dL (18 umol/L) but ≤ 0.5 mg/dL (44 umol/L) above baseline: | 
 1. Continue Dabrafenib and re-check serum creatinine within 1 week 2. If subject has fever ($T \geq 38.5$C): treat pyrexia as per guidelines (please note NSAIDs can induce renal insufficiency, especially in subjects with dehydration); encourage oral fluids 3. If elevation in serum creatinine persists beyond 1 week, please contact study coordinator |
| For subjects with serum creatinine rise >0.5 mg/dL (44 umol/L) above baseline or serum creatinine >2 mg/dL (> 177 umol/L) | 
 1. Interrupt Dabrafenib 2. If subject has fever ($T \geq 38.5$C): treat pyrexia as per guidelines (please note NSAIDs can induce renal insufficiency, especially in subjects with dehydration); consider IV hydration 3. Follow serum creatinine at least twice weekly (or consider hospitalization if serum creatinine cannot be monitored frequently) 4. Consider renal consultation 5. If serum creatinine returns to baseline, may restart study treatment at the same dose, or reduced by one dose level at the investigator's discretion. 6. Consider renal biopsy if clinically indicated, for example: 
 a. Renal insufficiency persists despite volume repletion b. Subject has new rash or signs of hypersensitivity (such as elevated eosinophil count) 7. Approval of PI is required to re-initiate therapy if 
 c. Subject's serum creatinine has not returned to baseline d. There is evidence of thrombotic microangiopathy |

